4.2. Number of Participants

We proposed to recruit approximately 244 eligible cases that will be placed in 3 treatment arms: inpatient, in-person OCIC and telehealth CIS. We expect to recruit a small proportion of the suicidal adolescent group in the ED or who receive crisis assessment from telehealth or via phone. To test Aim 1, we will use Cox proportional regression model (CPR) to test whether the telehealth only CIS; outpatient, in-person CIS; and in-patient CIS groups have different incidence rates for recurrent episodes within 3 months. We expect that the sample sizes for the three arms will be *at least* 75, 75, and 70 respectively. To test Aims 2 and 3, we will use the generalized linear model (GLM) to evaluate whether telehealth only CIS; outpatient, in-person CIS; and in-patient CIS groups have different levels of changes in emotional arousal (Aim 2) and treatment satisfaction (Aim 3) at 3 months, after adjusting for several covariates (e.g., age, gender, triage “location”). For CPR, we will have power for our pilot study greater than 0.70 assuming a hazard ratio of 2.8 and greater than 0.8 for our GLM analyses assuming $f^2 = 0.1$ and correcting for multiple comparisons.

Recruitment Plan for Prospective Studies

. Estimated number of potentially eligible study participants	500
. Total number of study participants expected to be screened:	300
. Total number of study participants expected to be eligible of those screened:	270
. Target sample size (use same number stated in milestones):	244
. Total number of practices or centers that will enroll participants:	4
. Projected month first participant enrolled (month after project initiation):	2nd Month

• Projected month last participant enrolled (month after project initiation):	10 th Month
• Projected rate of enrollment (anticipated number enrolled per month of enrollment period):	2- 10/month
• Estimated percentage of participant dropout:	10%

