7.2. Lost to Follow Up

A participant will be considered lost to follow-up if he or she repeatedly fails to complete surveys and/or fails to return for scheduled visits and is unable to be contacted by the study site.

The following actions must be taken if a participant fails to return to the clinic for a required study visit or fails to complete the surveys/questions that occur about every 2 weeks:

- The site must attempt to contact the participant and reschedule the missed survey or visit as soon as possible and counsel the participant on the importance of maintaining the assigned survey or visit schedule and ascertain whether or not the participant wishes to and/or should continue in the study. Text messaging may be used as a method of communication with the participant to encourage survey completion and/or to notify that further communication by phone or in person is needed.
- In cases in which the participant is deemed lost to follow up, the investigator or designee must make every effort to regain contact with the participant (where possible, 3 telephone calls and, if necessary, a certified letter to the participant's last known mailing address or local equivalent methods). These contact attempts should be documented in the participant's research record.

- Should the participant continue to be unreachable, he/she will be considered to have withdrawn from the study with a primary reason of lost to follow-up.

8. Study Assessments and Procedures

- Study procedures and their timing are summarized in the SoE (Appendix). Surveys are administered and requested for completion every 2 weeks. Data will be collected upon return of surveys. If surveys are not completed within 10 days of milestone window, that window will be skipped and study team will request data at the next milestone window.
- Baseline data and follow surveys/forms will be completed through REDCap and/or paper forms. CCHMC REDCap can collect almost any type of data, and is particularly designed to support online and offline data capture for research studies and operations.
- Adherence to the study design requirements, including those specified in the SoE, is essential and required for study conduct.

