- All screening evaluations must be completed and reviewed to confirm that potential participants meet all eligibility criteria. The investigator will maintain a screening log to record details of all participants screened and to confirm eligibility or record reasons for screening failure, as applicable.
- Time to first recurrence of a suicidal event and number of suicidal events will be measured with the Suicidal Event Form for START (appendix), a short supplemental form (developed by our team), at baseline and every two weeks (see Schedule of Events; appendix)
- Severity of suicidal ideation will be measured with the self-report scale: CHRT-SR (appendix) at baseline and every two weeks (see Schedule of Events; appendix).
- The Suicidal Treatment AlteRnatives for Teens (START)-Clinical Features (CF) form (appendix), a short supplemental form with 13 questions (developed by our team), will be completed at baseline (within 72 hours of admission to inpatient or OCIC) and every two weeks to monitor substance use based on information from patient, parent, and/or EHR.
- The C-SSRS Self-Report form, included in the CF survey, will be completed at baseline and every 2 weeks by the participant to assess for suicidal thoughts and behaviors.
- Satisfaction with Life (SL) will be measured with self-report scales including the PROMIS Short Form v 1.0-General Life Satisfaction-Short Form 5a (to assess the parent's well-being), PROMIS Parent-Proxy Life Satisfaction-Short Form 8a, and PROMIS Pediatric Life Satisfaction-Short Form 4a every 2 weeks.
- Treatment satisfaction (TS) data about, telehealth CIS, OCIC and inpatient psychiatry will be collected only after two weeks and/or subsequent to completion of inpatient psychiatry or OCIC. TS will be measured once with the Client Satisfaction Questionnaire (CSQ-8) 95 after completion of telehealth, OCIC or inpatient treatment which is typically completed by week 3 (but could be completed by week 2 to week 6).
- COVID-19 Impact survey will be completed at week 2 and will gather information regarding the impact of the pandemic on the participant and families social, emotional, and economic functioning.

- The Self-Assessment Manikin (SAM) questionnaire will be completed at baseline and week 12 follow up survey.

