increased risk of serious suicide attempts and suicide.⁶¹⁻⁶³ The cultural context of adolescent suicidal behavior and help-seeking is important and differs among races and ethnic groups.¹⁰⁵ For example, in the Hispanic community, families are much less likely to seek mental health professionals in help seeking and prefer to rely on family first.⁶⁴ Ethnic groups and races differ in rates of adolescent suicidal behaviors.^{105, 106} However, the gap has been decreasing between white adolescent suicides and African American suicides due to an increase in male African American deaths by suicide.⁶⁵⁻⁶⁷ Living situation (living with one biological parent, two biological parents, a stepparent, a relative, or other) is an important HTE for adolescents because living with one parent or the presence of a stepparent was correlated with an increased risk of suicidal thoughts and suicide attempts by adolescents.^{68, 69}

The analysis plan:

To test Aim 1, we will use Cox proportional regression model (CPR) to test whether the telehealth only CIS; outpatient, in-person CIS; and in-patient CIS groups have different incidence rates for recurrent episodes within 3 months. We expect that the sample sizes for the three arms will be *at least* 75, 75, and 70 respectively. To evaluate Aims 2 and 3, we will use the generalized linear model (GLM) to evaluate whether telehealth only CIS; outpatient, in-person CIS; and in-patient CIS groups have different levels of changes in emotional arousal (Aim 2) and treatment satisfaction (Aim 3) at 3 months, after adjusting for several covariates (e.g., age, gender, triage “location”). For CPR, we will have power for our pilot study greater than 0.70 assuming a hazard ratio of 2.8 and greater than 0.8 for our GLM analyses assuming $f^2 = 0.1$ and correcting for multiple comparisons.

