11.1. Appendix 1: Schedule of Events (SoE) / Milestones

Schedule of Events

Measures	Visit (Weeks)											
	Baseline	2	4	6	8	10	12	14	16	18	20	22
Age/Gender/Gender Identity/Insurance Type (Public, Private, No Insurance)/Ethnicity (Hispanic, Non Hispanic)/ Race (African American, Non African American)/ Living Situation (One Parent, Both Parents, Other)												
Demographics Form	x											
Severity of Suicidal Ideation												
CHRT-SR (self-report)-14 item	x	x	x	x	x	x	x	x	x	x	x	x
Suicidal Events												
Suicidal Event Form for START	x	x	x	x	x	x	x	x	x	x	x	x
Substance Use												
Clinical Features (CF)	x	x	x	x	x	x	x	x	x	x	x	x
Treatment Satisfaction												
Client Satisfaction Questionnaire (CSQ-8)		x										
Satisfaction with Life												
PROMIS Short Form-Life Satisfaction (SL)	x	x	x	x	x	x	x	x	x	x	x	x
PROMIS Parent-Proxy SL-Short Form 8a	x	x	x	x	x	x	x	x	x	x	x	x
PROMIS Pediatric SL-Short Form 4a	x	x	x	x	x	x	x	x	x	x	x	x
Other												
COVID-19 Survey		x										
Self Assessment Manikin (SAM)	x						x

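### The Aim 3 analysis of treatment satisfaction is set at 3 months, but the only CSQ-8 is planned after treatment or at week 2, and these two collection rules conflict for patients still in treatment at week 2.

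*Combined protocol and SAP*

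**What the plan says.** **Analysis.** Section 4.2 introduces the model: "To test Aims 2 and 3, we will use the generalized linear model (GLM) to evaluate" the arms. Sections 4.2 and 9.2.3 both give its outcomes as "different levels of changes in emotional arousal (Aim 2) and treatment satisfaction (Aim 3) at 3 months".

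**Collection, section 8.** One sentence has satisfaction data "collected only after two weeks and/or subsequent to completion of inpatient psychiatry or OCIC"; telehealth is missing from its completion clause. The next says "TS will be measured once with the Client Satisfaction Questionnaire (CSQ-8") after telehealth, OCIC or inpatient treatment is completed, "which is typically completed by week 3 (but could be completed by week 2 to week 6").

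**Collection, Schedule of Events (Appendix 1).** The CSQ-8 row has a single mark, at week 2. The COVID-19 survey has its mark in the same column, and section 8 places that survey at week 2, which confirms the reading.

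**Status of the schedule.** Section 8 states: "Adherence to the study design requirements, including those specified in the SoE, is essential and required for study conduct".

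**Length of care, section 6.** Inpatient stays are listed as 6 to 8 days. OCIC and telehealth are listed as 4 to 6 weeks at Dallas, 1 to 6 weeks at Cincinnati and Columbus, and 3 visits (OCIC) or 1 to 3 visits (telehealth) at New York.

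**The concern.** The wording of the model fits Aim 2, because the Self-Assessment Manikin is collected at baseline and week 12. It does not fit Aim 3. No CSQ-8 exists at 3 months, and none at baseline from which to form a change. Whether the word changes is meant to cover satisfaction is unclear from the grammar; if it is, the outcome cannot be computed.

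The second problem is the collection rule. SA3 compares telehealth with inpatient care and with in-person OCIC. A form sent to everyone at week 2 reaches inpatients after discharge but reaches many outpatients during their course. A telehealth versus inpatient difference could then mix satisfaction with stage of care. The imbalance lies within a site, so adjusting for triage location would not remove it. The time-point label can be corrected in the SAP. The week of collection cannot be changed once forms are returned.

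**Working it through.** **1. Stated figures.** The claims attached to continuous outcomes reproduce closely enough, so power is not in dispute.
- Section 9.1, two groups, d = 0.5, n = 75 and 70: noncentrality 0.5 × √(75 × 70 / 145) = 3.01. The two-sided t test at 0.05 gives power 0.848 (stated: 0.84).
- Section 9.2.3, f² = 0.1, three groups, N = 75 + 75 + 70 = 220: λ = 0.1 × 220 = 22. The F test on 2 and 217 df gives 0.99 at 0.05 and 0.97 at 0.05/3 (stated: above 0.8 after correcting for multiple comparisons).

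**2. Time points side by side.**

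| Place | Time point for satisfaction |
|---|---|
| Sections 4.2 and 9.2.3 | 3 months |
| Section 8 | once, after completion (typically week 3, range weeks 2 to 6), or after two weeks and/or completion |
| Schedule of Events | week 2 only |

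CSQ-8 forms planned at baseline: 0. At week 12: 0. The gap to week 12 is 12 − 2 = 10 weeks under the schedule. It is 12 − 6 = 6 to 12 − 2 = 10 weeks if the range in section 8 is taken as the time of rating.

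**3. Who is still in treatment at week 2.** Take baseline as day 0. Section 4.1 puts baseline data within 72 hours of admission, so I let inpatient admission fall on day −3 to 0. Section 6 expects outpatient care to be scheduled within 7 business days, taken here as up to 11 calendar days, so I let outpatient care start on day −3 to 11.
- Inpatients with listed stays are 14 − 8 = 6 to 14 + 3 − 6 = 11 days past discharge on day 14.
- The earliest that a Dallas 4-week course can end is day −3 + 28 = 25. Every listed Dallas course is therefore unfinished on day 14. Section 8 also says "If surveys are not completed within 10 days of milestone window, that window will be skipped"; read as 10 days after day 14, a form returned on day 24 still precedes day 25.
- Cincinnati and Columbus: unknown. Courses are listed as up to 6 weeks but average 1 to 3 sessions.
- New York: unknown. With weekly visits (assumed), a 3-visit course is finished by day 14 only if it started by day 0.
- OCIC versus telehealth: listed lengths nearly match within each site, so this contrast is little affected.

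**4. Illustration with only Dallas affected.** The synopsis gives 61 of 244 participants per site, or 25%. With arms spread evenly over sites (assumed), 25% of outpatients rate mid-course.

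Bias = 0.25 × shift, where the shift is the mid-course minus post-treatment difference in SD units. The documents do not give it, so 0, 0.2 and 0.5 SD are assumed. Rejection rates are for a two-sided t test, 75 versus 70, with no true difference.

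| Assumed shift | Bias | Rejection at 0.05 | Rejection at 0.05/3 |
|---|---|---|---|
| 0 | 0 | 5.0% | 1.7% |
| 0.2 SD | 0.05 SD | 6.0% | 2.2% |
| 0.5 SD | 0.125 SD | 11.6% | 5.0% |

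The 0.05/3 column is one possible form of the multiplicity correction that section 9.2.3 mentions without specifying.

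**The case against.** The strongest reply is that the 3-month label is a wording slip. Section 9.2 calls itself a summary and leaves the details to an SAP finalized before database lock. The CSQ-8 is a secondary outcome in what section 9.2.3 calls a pilot study, and a model on the single score works without loss of power. That stands for the label, but a later SAP cannot repair the week of collection.

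It can also be said that section 8 plainly intends a rating after treatment, that its compliance sentence covers the design requirements as a whole rather than placing the schedule above section 8, and that week 2 may be only the earliest allowed point. This is a fair reading and it narrows the conflict to patients still in treatment at week 2. It does not remove the conflict: the schedule offers no later CSQ-8 slot, and the and/or sentence permits a rating after two weeks without completion.

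A reader might infer more than the documents support:
- **That week-2 collection would bias the comparison.** Bias also requires satisfaction to differ between mid-course and completion, and the documents do not say that it does, or in which direction.
- **That the effect lies mainly at Dallas.** Dallas is the only site where every listed outpatient course runs past week 2. If more than half of Cincinnati and Columbus outpatients were also mid-course, however, Dallas would supply less than half of the pooled effect.
- **That a ceiling can be put on the affected share.** Counting Dallas, Cincinnati and Columbus in full gives 75%, but this is no upper bound, since New York 3-visit courses can also pass day 14. It also sits badly with averages of 1 to 3 sessions. Large error rates built on it are not supported.

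Finally, a post-treatment rule has its own imbalance, because time since the crisis then differs by arm. That stands and is taken up under the fix.

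**Conclusion.** The inconsistency holds on the documents' own wording and needs no assumption. Aim 3 has no data at 3 months and no change score, and the collection rule is unsettled for patients still in treatment at week 2. The possible bias is conditional on sites following week 2 and on mid-course satisfaction differing from satisfaction after treatment. With Dallas alone affected and a shift of 0 to 0.5 SD, the effect is modest: at most 0.125 SD, against the 0.5 SD used for power in section 9.1, and a false-positive rate that does not exceed about 5% if 0.05/3 is used. It would be larger if outpatients elsewhere were also mid-course, by an amount that cannot be determined from the documents. For a secondary outcome this should be corrected, and before more forms come in.

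**What to change.** - Define the Aim 3 outcome as the level of the single CSQ-8 score, collected at the first 2-weekly milestone after treatment ends, in every arm.
- State one fallback milestone for participants with no recorded end date. Week 8 would cover the longest listed course: a 6-week course starting on day 11 ends on day 53, before day 56.
- Align sections 4.2, 8 and 9.2.3 and the Schedule of Events. For Aim 3, remove the change wording and the 3-month time point. Replace the week-2-only mark, and say whether weeks 2 to 6 in section 8 describes when treatment ends or when the form is due.
- Record the treatment-end date. Report by arm the days from treatment end, and from baseline, to the CSQ-8.

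**Cost.** One date field per participant, a REDCap trigger based on it, and wording edits in four places. No added questionnaire or visit, and no change in care.

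**Downside.** Time since the crisis will still differ by arm: about week 2 for inpatients, weeks 4 to 8 for a 4 to 6 week course. Those who leave early may rate some weeks after leaving; section 2.2 reports 81.04% completion in the earlier Dallas OCIC cohort, so about 19% did not complete. Reporting both intervals lets readers judge this.
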